3.2 Efficacy and Safety Variables

The primary efficacy variable is the ADAScog-11 score at Week 26.

The secondary efficacy variables include:

- ADAScog-11 at Weeks 4 and 13
- CDR-SB at Weeks 4, 13, and 26
- MMSE at Weeks 4, 13, and 26
- ADCS-ADL at Weeks 4, 13, and 26
- NPI at Weeks 4, 13, and 26
- C-SDD at Weeks 4, 13, and 26

The safety variables include AEs reported throughout the study and blood pressure measurement, ECGs, physical and neurological examination, and assessment of suicidality using the C-SSRS at Weeks 4, 13, 26, and 30. Blood and urine samples for

laboratory evaluations will be collected at screening, baseline, Weeks 4 (Liver Function Test only), 13, 26 and 30.

4 STATISTICAL METHODS

4.1 Data Quality Assurance

All tables, figures and data listings to be included in the report will be independently checked for consistency, integrity, and in accordance with standard [REDACTED] procedures.

4.2 General Presentation Considerations

This section describes the analysis and data conventions that will be utilized for this study. All statistical analyses and summary information are to be generated according to this SAP. Any deviations from this SAP will be documented in the clinical study report (CSR).

4.2.1 General Definitions

Unless otherwise stated, baseline measurement is defined as the latest, valid pre-dose assessment available. 'End of Study' is defined as the last available post-treatment assessment. A subject who completes all study visits up to Week 30, will be considered to have completed the study. For evaluation of efficacy, a completed subject is defined as any subject who completes all visits up to Week 26.

4.2.2 Visit Windows

Assessments will be classified based on the visit information reflected on the eCRF. Assessments taken outside of protocol allowable windows will be assigned based on the closest scheduled visit. If there are assessments recorded on a day that is equidistant between two visits, the assessments will be attributed to the later visit. The only exception to this rule is for assessments recorded between Baseline and Week 4. Any assessment recorded after the Baseline visit will be mapped to Week 4 even if the day is closer to the Baseline visit. The timetable of visits is given in Section 7.1 in the protocol. Nominal study visits (Weeks relative to Baseline) will be used to summarize data presented by visit.

If subjects have more than one observation for a given time point, the average of the measurements will be used. This rule applies to efficacy data. For safety data, unless otherwise specified, if there is a repeated evaluation, the worst value will be used. If values are equal, the latest repeated (latest) value will be used.

If subjects withdraw early from the study, all study assessments at the early withdrawal visit will be assigned based on the rules described above. That is, they will be assigned to the closest scheduled visit. Data from subjects who discontinue but return after 4 weeks for the follow-up visit will be summarized with the Week 30 visits.

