6.1.1 Primary Efficacy Variable

The primary efficacy variable for the study is the ADAS-Cog.

The ADAS-Cog is a brief measure of cognition, including word recall, commands, constructional praxis, naming objects and fingers, ideational praxis, orientation, word recognition, remembering test instructions, spoken language ability, word-finding difficulty, and comprehension of spoken language.

The ADAS-Cog will be administered to the subject and scored by a qualified, trained rater at screening, baseline and at Weeks 4, 13 and 26 as indicated in the Schedule of Procedures ([Table 3](#)).

Further details regarding the assessment are provided in [Appendix 1](#).

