7.2.5 Week 26 Visit (Visit 5, Day 182)

The following procedures will be performed at Week 26 (Day 182±3 days) of the study:

- AE review
- Concomitant medications review
- Plasma sample for measurement of SUVN-502, M1 of SUVN-502, donepezil and memantine levels
- Study drug compliance check and dispensation
- Blood and urine samples for clinical laboratory tests, including pregnancy test for women of childbearing potential
- Physical and neurological examinations
- Blood pressure measurement
- MMSE
- ADAS-Cog
- CDR-SB, ADCS-ADL, NPI and C-SDD
- C-SSRS (since last visit version)
- ECG 3 hours post-treatment

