4	Moderately severe	= subject has difficulty more than 50% of the time
5	Severe	= one or two word utterance; fluent, but empty speech; mute

The total score for the ADAScog-11 is the sum of the above 11 items. The maximum score is 70 points. A lower score indicates a better performance.

If any item is not administered because the subject is too cognitively impaired to complete, then the subjects receives the maximum amount of points for that item. Any other reason for not administering the item on the eCRF will be left as missing. Handling of missing items in the ADAScog-11 is summarized in [Section 4.7.1.2](#).

Summary

ADAScog-11 scores will be summarized by treatment group and visit in terms of absolute values and changes from baseline, both for the observed case and LOCF analyses.

A listing of observed and change from Baseline value will be provided.

Analysis

A MMRM will be used to test the hypotheses stated in [Section 4.7.1](#) that there is no difference between SUVN-502 and placebo in the mean change from baseline at Week 26 for the ADAScog-11 score. The LS means of each treatment group, and the differences between each SUVN-502 dose group and placebo will be reported for Weeks 4, 13, and 26, along with the corresponding 95% confidence intervals and p-values.

The change from baseline score at each scheduled post-baseline visit (according to the Study Schedule) during the treatment period will be the dependent variable. The model will include the fixed effects of treatment, week, treatment-by-week interaction, and APO-E status (carrier- one allele, carrier- two alleles, and non-carrier), as well as a continuous covariates of baseline score, the baseline score-by-week interaction, age, and Baseline MMSE score. Pooled site, as defined in [Section 4.2.4](#), will be included as a random effect. Week will be considered a categorical variable with values equal to the visit numbers at which the scales were assessed. An unstructured covariance matrix will

initially be used to model the within-subject variance-covariance errors. The following SAS code will be used to perform the analyses:

```
PROC MIXED;  
CLASS treat week subjid apoe site;  
MODEL outcome = treat week treat*week base base*week apoe mmse_base age /  
          DDFM=kr;  
RANDOM site;  
REPEATED week / SUBJECT=subjid TYPE=UN;  
LSMEANS treat/ cl diff;  
RUN;
```

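### Read literally, the SAP's nearest-visit rule moves a Visit 5 ADAScog-11 taken on Day 196 or later to Week 30, leaving an observed Week 26 value out of the primary comparison

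*SAP*

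**What the plan says.** SAP 4.2.2 starts from the site's visit label: "Assessments will be classified based on the visit information reflected on the eCRF". It then overrides that label for late or early assessments: "Assessments taken outside of protocol allowable windows will be assigned based on the closest scheduled visit". For ties: "If there are assessments recorded on a day that is equidistant between two visits, the assessments will be attributed to the later visit". One departure is allowed: "The only exception to this rule is for assessments recorded between Baseline and Week 4". The visit days come from the protocol: "The timetable of visits is given in Section 7.1 in the protocol". That timetable (protocol Table 3) includes the Week 30 follow-up visit on Day 210±2. Protocol 7.2.5 sets "Week 26 (Day 182±3 days) of the study".

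Protocol 6.1.1 has the ADAS-Cog given by a "trained rater at screening, baseline and at Weeks 4, 13 and 26". Table 3 and the Week 30 procedure list in protocol 7.2.6 do not include it, and they also omit MMSE, CDR-SB, ADCS-ADL and NPI. C-SDD, laboratory tests and ECG are done at both Week 26 and Week 30.

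On the primary model, SAP 4.7.2 says: "The change from baseline score at each scheduled post-baseline visit (according to the Study Schedule) during the treatment period will be the dependent variable". Results are reported for Weeks 4, 13 and 26. SAP 4.7.1.2 leaves missing totals missing in the primary analysis.

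**The concern.** The mapping rule does not ask whether the nearest visit is one at which the scale is given. Between most visits this does little harm: a Week 13 score taken late enough to be called Week 26 is still in the model. Between Week 26 and Week 30 it matters, because Week 30 is outside the model. A participant who attends Visit 5 very late has a measured primary outcome, and SAP 4.2.1 counts that participant as a completer for efficacy, yet the Week 26 cell is empty. The z-score LOCF sensitivity analysis would then impute a value from an earlier visit although a real one exists.

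Safety and C-SDD data have a different problem. Protocol 6.2.4 times the Week 26 ECG at about peak drug concentration, while Week 30 follows four weeks of placebo. If a late Visit 5 is relabelled Week 30, its values share that visit with the true follow-up. C-SDD is then averaged across the two under SAP 4.2.2, and for laboratory and ECG data the worst value is kept. End-of-treatment values could be reported as washout values.

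**Working it through.** **1. Where the boundary falls.** Inputs: Week 26 target Day 182 with window Days 179–185 (protocol 7.2.5); Week 30 target Day 210 with window Days 208–212 (protocol 7.2.6); tie rule from SAP 4.2.2.

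Midpoint = (182 + 210) / 2 = Day 196.

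| Day of Visit 5 | Distance to 182 | Distance to 210 | Rule as written | Only visits that schedule the scale |
|---|---|---|---|---|
| 186 | 4 | 24 | Week 26 | Week 26 |
| 195 | 13 | 15 | Week 26 | Week 26 |
| 196 | 14 | 14 (tie, later visit) | Week 30 | Week 26 |
| 197 | 15 | 13 | Week 30 | Week 26 |
| 210 | 28 | 0 | Week 30 | Week 26 |

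The rule affects Visit 5 only when it is at least 196 − 182 = 14 days after target, or 196 − 185 = 11 days past the window.

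**2. What happens to the score.** SAP 4.2.2 labels it Week 30. SAP 4.7.2 models treatment-period visits and reports Weeks 4, 13 and 26. SAP 4.7.1.2 leaves Week 26 missing. Together these leave the observed value out of the Week 26 contrast.

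**3. The plan's sample size, reproduced.** Inputs from SAP 4.10 and protocol 8.9: difference 2, SD 6, two-sided 5%, at least 80% power, dropout up to 20%, 179 per arm.

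- Normal approximation: n = 2 × (1.96 + 0.8416)² × 6² / 2² = 141.3, so 142 per arm; 142 / 0.8 = 177.5, so 178 per arm and 534 in total.
- t-test: 143 per arm (power 80.2%; 142 gives 79.9%); 143 / 0.8 = 178.75, so 179 per arm and 537 in total, the stated figure.

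**4. Size of the loss.** Expected completers = 179 × 0.8 = 143.2 per arm. The rate of visits 14 or more days late is not in the documents, so a range is assumed. Power = Φ(2 / (6 × √(2/n)) − 1.96), treating each affected participant as wholly lost:

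| Assumed share affected | Values lost per arm | n left per arm | Power |
|---|---|---|---|
| 0% | 0 | 143.2 | 80.5% |
| 1% | 1.4 | 141.8 | 80.1% |
| 2% | 2.9 | 140.3 | 79.7% |
| 3% | 4.3 | 138.9 | 79.3% |

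The cost over 1–3% runs from 0.4 to 1.2 percentage points. This is an upper figure, because in the MMRM the same participants still contribute Weeks 4 and 13.

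**5. Could a participant still be on drug by then?** Protocol 5.3.1 gives bottles of 35 tablets. Day 91 to Day 182 needs 91 tablets, so whole-bottle dispensing (an assumption; protocol 5.2.1 says only that enough is given to reach the next visit) means 3 × 35 = 105. Taken daily from Day 91, these last to Day 91 + 105 − 1 = Day 195. On that supply, a score after Day 196 follows at least one day without double-blind drug.

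**The case against.** The SAP never states that such a score is dropped. The rule begins with the eCRF label, and SAP 4.7.2 ties the modelled visits to the study schedule. A programmer could therefore take the closest scheduled visit to mean the closest one at which that scale is scheduled, and keep the score at Week 26. That reading is possible, but it is not written, and naming a single exception to the rule weighs against adding another. If two programmers can disagree on who has a Week 26 value, the text needs settling.

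It can also be argued that keeping very late scores out of Week 26 is reasonable windowing. This stands in part: on the inferred supply, scores after Day 196 may be off drug, so simply moving them back to Week 26 is not free of cost. But the SAP sets no upper limit for Week 26 on that ground; the cut-off is a by-product of the Week 30 date.

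On the secondary effects, C-SDD at Week 30 is not an efficacy variable in SAP 3.2, so averaging there alters no tested Week 30 comparison, although the Week 26 C-SDD value is still lost. For laboratory and ECG data only the by-visit labels move; SAP 4.8.4 also summarises the liver criteria overall, and treatment-emergent events do not depend on visit mapping. These points stand and limit the harm.

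SAP 4.11 allows changes after blinded review. That is a way to make the correction, not a reason to leave the rule as it is.

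**Conclusion.** Applied as written, SAP 4.2.2 takes an observed Visit 5 value on Day 196 or later out of the Week 26 comparison for ADAScog-11 and four secondary scales, and places late Visit 5 C-SDD, laboratory and ECG values in the post-washout visit. The boundary follows from the documents' own visit days and needs no assumption. The size does: over an assumed 1–3% of about 143 completers per arm, 1–4 Week 26 values per arm are lost, with at most about 1 percentage point of power at stake. The 20% dropout behind the 143 is itself a ceiling.

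A reader might infer more, and the documents do not support it:

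- **That affected participants leave the primary analysis altogether.** They do not; their Week 4 and Week 13 scores remain.
- **That the trial becomes underpowered.** No late-visit rate is given, and the calculated loss is small and overstated for an MMRM.
- **That the lost scores are all on-treatment.** The inferred supply ends on Day 195.
- **That the result is biased.** Nothing in the documents shows that late visits differ by arm.

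The reason to act is that a prespecified rule should not set aside observed primary data or mislabel end-of-treatment safety data when a small wording change prevents it.

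**What to change.** - In SAP 4.2.2, replace 'closest scheduled visit' with 'closest visit at which protocol Table 3 schedules that assessment'. Post-baseline ADAScog-11, MMSE, CDR-SB, ADCS-ADL and NPI then map only to Weeks 4, 13 and 26.
- State that C-SDD and safety data recorded at eCRF Visit 5 before the first washout tablet stay at Week 26.
- Add a sensitivity analysis of the primary endpoint that excludes Week 26 scores taken on Day 196 or later, or taken more than a prespecified number of days after the last double-blind dose. The first criterion reproduces the present Week 26/Week 30 boundary, so the effect of the change can be seen.

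The cost is a few sentences and one extra model run, settled before unblinding and database lock. The downside is that a few primary Week 26 values will come from later than planned, some possibly off drug; the sensitivity analysis shows whether that matters.

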4.2.3 Handling of Outliers

Any outliers that are detected statistically during the blind review of the data will be investigated. If necessary, queries will be issued to the Investigator, to either correct or confirm the reason for the outlier. If any outlier is confirmed, the actual value will be included in the analysis.

4.2.4 Site Pooling Strategy

Site will be included in the model. Sites with fewer than 2 subjects in each treatment group will be pooled for analysis starting with the largest study site and pooling with the site that best balances that site's randomization until each pooled site meets the requirement for at least 2 subjects per treatment group. If the last pooled site does not have 2 subjects per treatment group, it will be combined with the next smallest pooled site.

4.2.5 Presentation of Descriptive and Inferential Statistics

Continuous data will be summarized in terms of the mean, standard deviation (SD), lower quartile, median, upper quartile, minimum, maximum and number of non-missing observations, unless otherwise stated. The minimum and maximum will be reported to the same number of decimal places as the raw data recorded in the database. The mean, median and quartiles will be reported to one more decimal place than the raw data recorded in the database. The SD (and standard error if applicable) will be reported to two more decimal places than the raw data recorded in the database. In general, the maximum number of decimal places reported shall be four for any summary statistic.

Categorical data will be summarized in terms of the number of subjects providing data at the relevant time point (n), frequency counts, and percentages. Any planned collapsing of categories will be detailed in the SAP text and the data displays.

Percentages will be presented to one decimal place. If the percentage is 100%, decimal will not be presented. Percentages will not be presented for zero counts. Percentages will be calculated using n from each treatment group as the denominator, unless otherwise specified in the data displays.

Changes from baseline in categorical data will be summarized using shift tables where appropriate.

Each SUVN-502 dose group comparison with the placebo group will be made at a 2-sided significance level of $\alpha=0.05$. For the secondary endpoints, each SUVN-502 dose group comparison with the placebo group will also be made at a 2-sided significance level of $\alpha=0.05$. All null hypotheses of treatment comparisons will be set as no treatment difference. Confidence intervals (CIs) produced will be 2-sided with 95% confidence level unless specifically stated otherwise.

In general, p-values greater than or equal to 0.001 will be presented to 3 decimal places. P-values less than 0.001 will be presented as “<0.001”, and p-values greater than 0.999 will be presented as “>0.999”. A check will be performed for p-values greater than 0.999.

Confidence intervals will be presented to 1 more decimal place than the mean.

Listings will be sorted by subject within each treatment group.

All analyses will be conducted using SAS® version 9.3 or a later version in a secure and validated environment.

4.3 Study Subjects

4.3.1 Disposition of Subjects

Information on the disposition of all subjects who enter the study will be provided, from screening to study completion (Week 30).

The following subject data will be presented by treatment group, including overall categories:

- The number of subjects screened (overall only)
- The number of subjects randomized

- The number and percent of subjects randomized who were intended to be treated with study medication
- The number and percent of subjects treated
- The number and percent who completed up to Week 26 and Week 30 follow-up
- The number and percent who completed up to Week 26 but not Week 30 follow-up
- The number and percent of subjects who withdrew from study prematurely but took placebo and completed Week 30 follow-up
- The number and percent of subjects who withdrew from study prematurely but completed Week 30 follow-up (retrieved dropouts)
- The number and percent of subject who withdrew from study prematurely and did not complete follow-up
- Time to discontinuation

Percentages of subjects will be based on the number of subjects randomized in each treatment group as 100%.

The number and percentage of subjects who prematurely withdrew during the study will be presented by reason for discontinuation. Time to study discontinuation will be presented by treatment group as the cumulative proportion of dropouts up to each visit.

In addition, subject listings will be provided for subjects who discontinued the study early (post-randomization) with reason for discontinuation.

4.3.2 Protocol Deviations

Protocol deviations will be identified on an ongoing basis by the clinical study team based on the protocol deviation specification document (PDS) and assessed as ‘major’ and ‘minor’ in consultation with the Sponsor. This assessment will be done during blinded data review meetings (BDRMs), which will take place when pre-determined accrual targets are met and before disclosure of randomization codes. Major deviations from the protocol that may lead to confounding of efficacy results will result in the exclusion of a subject from the Evaluable Population (EP). The final determination of major protocol deviations and the exclusion of subjects from each of the analysis populations will be made prior to database lock and unblinding.

Unless decided otherwise during the BDRMs, the following will be major protocol deviations:

- Informed consent violation
- Did not have any assessment of the primary endpoint at any of the visits at which the scales were scheduled to be assessed
- Protocol violations of certain inclusion/exclusion criteria
- Had unqualified raters or raters with substantial scoring errors for the primary measures
- Was not compliant with regard to study drug or concomitant Alzheimer's disease medications
- Use of prohibited medication during the double-blind period that may influence the outcome of the study for the subject
- Subject met withdrawal criteria but not withdrawn
- Subject failed to report SAE or pregnancy

Protocol deviations will be provided in a listing. Major protocol deviations will be also be summarized by treatment group for all randomized subjects.

4.4 Analysis Populations

Three populations are defined for the analyses:

- Modified intent to treat (mITT) population: All randomized subjects who receive at least 1 dose of study medication and have 1 post-baseline evaluation of the primary efficacy variable. Subjects will be assigned to the group they were randomized.
- Evaluable Population (EP): [REDACTED]
[REDACTED]
[REDACTED]
[REDACTED]
[REDACTED]
- Safety Population (SP): All randomized subjects who receive at least 1 dose of study medication. Subjects will be assigned to the treatment group based on the actual treatment received.

All efficacy analyses will be performed on the mITT population and the EP. The primary efficacy analysis of the primary endpoint will be based on the mITT population and a secondary analysis of the primary endpoint will also be performed based upon the EP. All secondary endpoints will be analyzed using both the mITT population and the EP.

Safety analyses will be performed on the SP. If a subject takes more than 1 study drug for any period of time, that subject will be included in the analyses with the highest dose group taken.

Demographic and baseline characteristics will be evaluated for the mITT population. Additional summaries will be presented using the Safety Population.

The number of subjects in the different analysis populations will be summarized by treatment group, and overall.

The subjects excluded from each analysis set will be listed with the reason for exclusion.

4.5 Demographic and Other Baseline Characteristics and Medical History

4.5.1 Demographic, Baseline, and Other Characteristics

Demographic and baseline characteristics will be summarized for the mITT population by treatment group and overall. Summaries will include descriptive statistics for continuous and categorical measures. Subject characteristics to be presented include:

- Age
- Age group: <65 years, ≥65 years and <75 years, ≥75 years
- Gender
- Height (m)
- Weight (kg)
- Body Mass Index (BMI) (weight (kg)/[height (m)]²)
- Race
- APO-E4 carrier status (carrier one allele, carrier two alleles, non-carrier)
- Modified Hachinski Ischemic Score (MHIS) score
- Duration of AD (years)

Duration of AD will be calculated as: (date of Screening – date of AD diagnosis + 1)/365.25

- Duration of memantine (years)
- Duration of donepezil (years)
Duration of donepezil and memantine will be calculated as: (date of Screening – date of first dose + 1)/365.25
- Baseline severity of impairment as measured by ADAScog-11, CDR-SB, MMSE, ADCS-ADL, NPI, and C-SDD
- Baseline ADAScog-11 score (\leq median, $>$ median)
- Baseline MMSE score (12-15, 16-20)
- Concomitant Therapy: donepezil HCl and memantine HCl, donepezil HCl and Namenda XR®, Namzaric™

Age will be calculated as the number of complete years between a subject's birth date and the date of informed consent.

Subject listings of demographic and baseline characteristics will be provided.

